18.1.2 Poorly controlled diabetes mellitus and related medical non-compliance

Some participants may present with symptoms of hyperglycemia due to medical or dietary non-compliance. If there are symptoms of hyperglycemia, a finger stick will be done. For participants with elevated glucose levels >400 but < 500 as determined by glucometer monitoring will be asked to take their medications if available. If they have been non-complaint with their medications or have no medications with them, they will be treated with sliding scale regular insulin and referred back to their primary care provider for evaluation after completing their longitudinal visit. If they have no medication at home, in the interest of providing the best care possible, we will provide a prescription for their previously prescribed hypoglycemic agent or an appropriate drug if they are unable to provide the name of the drug previously taken. They will be referred to an appropriate provider for disease management. Participants with glucose >500 will be referred to the ER and their testing suspended. If they refuse ER transport, we will document their choice with an Against Medical Advice (AMA) note in the chart signed by the participant. We will treat with regular insulin and attempt to get the soonest appointment with their provider or a provider at an appropriate medical clinic. These participants will be contacted 30 days after the interrupted testing to assess their suitability for completion of their longitudinal visit.

Some participants may mistakenly take their hypoglycemic agents while they are fasting in preparation for their visit and become hypoglycemic despite being instructed the night

before the visit via telephone to bring their meds to take at the MRV after they have had their blood drawn and are ready for breakfast. Depending on their glucose level using finger stick glucometer monitoring we will administer glucotabs, oral juices or injectable glucagon. Testing will resume when patient is no longer hypoglycemic by finger stick glucometer monitoring.

18.1.3 Poorly controlled asthma/chronic obstructive pulmonary disease (COPD).

Participants at times are non-compliant with their medications or have run out of their prescriptions and present with or develop symptoms of wheezing or dyspnea. Participants with a pulse oximeter of 85-90% will receive albuterol nebulizer and/or oxygen as directed by the medical staff. If the subject's saturation does not return to 90% or greater after treatment and remains stable, the subject will be referred to the emergency room. Participants with pulse oximeter values <85% will be sent to the local emergency department. They will be recontacted in 30 days to reassess their suitability for reappointment.

18.1.4 Alcohol Withdrawal

Participants who exhibit early signs and symptoms of alcohol withdrawal during testing, will have their testing interrupted and a detailed history taken of their alcohol use. Participants with prior history of severe alcohol withdrawal will be sent to the emergency room. In some instances it may become necessary to give the participant an initial dose of short acting benzodiazepine to prevent further deterioration prior to the participant being transported to the nearest emergency room by the Emergency Medical System (EMS). Participants with no prior history of severe alcohol withdrawal will be discharged home after receiving counseling and referral to an alcoholic detox program. Participants will be re-contacted in 30 days to reassess their suitability for reappointment.

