We have determined that at times, it may be necessary to temporarily suspend the research visit for ethical and safety reasons to administer initial urgent care for treatment of significant symptoms and physical examination findings before the participant can be discharged home, to their medical provider or the local emergency department. Circumstances can become quite complicated when participants exercise their right to refuse transport to an emergency department, HANDLS staff may not be able to contact the participant's primary care provider for an urgent appointment or the participant may not have a regular physician. There are five clinical presentations that we anticipate occurring episodically at the time of the HANDLS longitudinal visit and below we outline the proposed participant safety and well-being actions that will occur in keeping with standard medical practice and ethics:

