18.1.1 Poorly controlled hypertension and related medical non-compliance

Some participants will have neglected to take their medications on the day of the exam despite being told the night before to take all anti-hypertensive medications and to bring all medications to the visit. This will result in an elevated screening blood pressure reading. Participants with values <200 systolic and <100 diastolic will be asked to take their medica-

tions immediately. Their blood pressure will be monitored for reduction upon which we will allow them to remain for the study visit. If there is no reduction in blood pressure they will be advised to take their mediation as directed and referred to their primary care physician for a blood pressure check for possible modification of their regimen. They will be re-contacted in 30 days to again assess their suitability for reappointment.

Some participants will be newly diagnosed or non-compliant and have no anti-hypertensive medication. These participants will not continue their visit; they will be referred to their primary care physician for evaluation and treatment if they have a primary care physician. If there is no primary care practitioner, we will provide information about appropriate medical clinics in the vicinity in the context of their insurance status and ability to pay. Social work assistance is available on staff to assist medical staff in navigating the financial assessments. If there is no reduction in blood pressure, their visit will be terminated and they will be advised to take their mediation as directed and referred to their primary care physician for a blood pressure check for possible modification of their regimen. They will be re-contacted in 30 days to again assess their suitability for reappointment.

Participants with SBP>200mmHg and/or a DBP >110mmHg will not continue with their visit and will be sent to the closest ER. If they decline, we will document their choice with an Against Medical Advice (AMA) note in the chart signed by the participant. However, in the interest of providing best available care, we will offer the alternate of administering Clon-idine and providing a prescription for standard antihypertensive medications and an appointment for follow-up at the appropriate medical venue. They will be re-contacted in 30 days to again assess their suitability for reappointment.

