18.1.5 Seizure Disorder

Participants with a known history of seizure disorder, who have a seizure while being testing, will have their testing for the day stopped. Depending upon the situation, EMS may be activated. Participants who have a singular seizure episode with full recovery will be discharged to their primary care provider. For participants who have repeated seizure episodes, EMS will be activated and the participant will be treated with short acting benzodiazepine prior to the EMS arrival. Participants will be re-contacted in 30 days to reassess their suitability for reappointment.

For all clinical presentations in sections 18.1 to 18.1.5 above:

Participants will be asked to sign an Against Medical Advice (AMA) note if they decline EMS and or transport to an emergency room or their primary care physician's office per study clinician's advice.

If a participant's study visit is terminated due to a medical problem identified on the MRV, the study team will attempt to re-contact participant within four days to follow up and determine the outcome of treatment recommendations.

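### Section 18.1.4 sends participants in early alcohol withdrawal home on the basis of history alone, with no condition on their present severity or stability

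*Protocol*

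**What the plan says.** Section 18.1.4 applies once early signs of withdrawal appear during testing. Testing stops and a detailed alcohol-use history is taken. Three provisions follow.

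- Participants with a past severe withdrawal go to the emergency room.
- A drug treatment is allowed before ambulance transport: "In some instances it may become necessary to give the participant an initial dose of short acting benzodiazepine to prevent further deterioration".
- For everyone else, "Participants with no prior history of severe alcohol withdrawal will be discharged home after receiving counseling and referral to an alcoholic detox program".

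All participants under this rule are contacted again at 30 days about reappointment.

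Two general texts surround the five clinical rules. Section 18.1.0 says that a visit may at times be suspended to give urgent care for significant symptoms and examination findings "before the participant can be discharged home, to their medical provider or the local emergency department". It introduces the five rules as consistent with ordinary medical practice and ethics. The text after 18.1.5, which applies to all five presentations, says "Participants will be asked to sign an Against Medical Advice (AMA) note if they decline EMS and or transport to an emergency room" on the study clinician's advice. It adds an attempted contact within four days when a visit is ended for a medical problem.

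**The concern.** The home-discharge sentence is mandatory and rests on one fact about the past. A first severe episode occurs, by definition, in someone with no earlier severe episode, so this criterion cannot pick it out. The word for early signs describes how a participant comes under the rule. It does not describe their state when they leave. The section itself foresees that some will get worse, since it provides a drug to prevent that.

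At stake is the safety of a participant without a severe history whose signs have not settled. Staff who apply the sentence literally would release that person. The next fixed contact is the attempt within four days, then the one at 30 days. Mild, stable participants are not affected.

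**Working it through.** No arithmetic applies, so the check is a comparison of the texts.

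**1. What decides the destination in 18.1.4.** Past severe withdrawal leads to the emergency room, and its absence leads home. No examination finding, vital sign, severity score or period of observation appears between the history and the discharge.

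**2. Who the benzodiazepine sentence covers.** It comes directly after the sentence on participants with a severe history, but speaks only of the participant. Two readings are possible.
- If it covers only those with the history, a worsening first episode has no emergency route within 18.1.4.
- If it covers everyone, a worsening participant without the history falls under both the ambulance sentence and the home sentence, and the section does not say which prevails.

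Either way, the text leaves the case unresolved.

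**3. Whether the general clauses settle it.** Section 18.1.0 permits urgent care and lists home as one of three destinations. It does not say that home discharge depends on the result of that care. The text after 18.1.5 assumes that the clinician may advise emergency transport, and says what to record if it is refused. It gives no criterion for advising it. Both can be followed together with 18.1.4, and neither limits the home sentence.

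**4. How the neighbouring rules are written.**

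| Section | Non-emergency path | What limits it |
|---|---|---|
| 18.1.1 Hypertension | Stay if pressure falls ("Their blood pressure will be monitored for reduction upon which we will allow them to remain for the study visit"); otherwise referral to primary care | Recovery for staying; only the entry blood-pressure band for referral |
| 18.1.2 High glucose | Medication or insulin, complete the visit, refer back | Only the entry band, above 400 and below 500 |
| 18.1.2 Low glucose | "Testing will resume when patient is no longer hypoglycemic by finger stick glucometer monitoring" | Recovery, though no emergency-room route is given |
| 18.1.3 Asthma/COPD | Treated at a saturation of 85-90% | Recovery: a participant whose saturation "does not return to 90% or greater after treatment and remains stable, the subject will be referred to the emergency room" |
| 18.1.4 Alcohol withdrawal | Home | Past history, and the entry wording on early signs |
| 18.1.5 Seizure | "Participants who have a singular seizure episode with full recovery will be discharged to their primary care provider" | Recovery |

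The sound comparators are 18.1.3 and 18.1.5. Both tie the non-emergency path to recovery, and 18.1.4 does not.

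**The case against.** The strongest reply is that 18.1.4 should be read with its surroundings. Section 18.1.0 puts urgent care for significant findings ahead of discharge and places all five rules within ordinary medical practice. The closing text assumes clinician-advised transport. Deterioration is already met by the benzodiazepine and ambulance sentence. A participant sent home would most naturally count as having had the visit ended for a medical problem, so the four-day contact would apply. On this view a competent clinician would not release an unstable participant.

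Much of this stands. A reader might infer that 18.1.4 contradicts the general clauses. The documents do not support that: 18.1.0 is permissive and itself names home as a destination, and the closing text concerns refused transport and follow-up. A reader might also infer that 18.1.4 is the only rule of the five not bounded by the participant's present state. That is too strong as well, because the referral path in 18.1.1 and the high-glucose path in 18.1.2 are limited only by an entry band, much as early signs limit 18.1.4. Nor does the remark in 18.1.0 on incomplete disclosure help, since it concerns current status at pre-visit screening and not past withdrawal.

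What the reply does not remove is the mandatory wording. The clinician's latitude has to be inferred from general text, while the specific sentence gives an instruction. Section 2.0.0 also commits the investigator to no deviation without prior agreement and approval, except to remove an immediate hazard. A clinician who keeps an unsettled participant should not have to rely on that exception.

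**Conclusion.** The point holds in a limited form. Section 18.1.4 makes home discharge depend on the absence of past severe withdrawal, with no condition on present severity or stability, and leaves the reach of its own emergency sentence unclear. The general clauses soften this without curing it.

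Its size is small: a minor correction to participant safety that is cheap to make. Clinician judgement would probably catch many of the cases concerned. The protocol gives no frequency for withdrawal during visits, so the number exposed cannot be estimated, and no study estimate or sample-size figure depends on it. The conclusion rests on the protocol text alone. The standard operating procedures in the Operations Manual (section 15.0.0) are not shown and may already contain a stability check, in which case the protocol should be brought into line with them.

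**What to change.** Amend 18.1.4 in two respects.

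1. Limit home discharge, with counselling and detox referral, to participants who have no past severe withdrawal and whom the study clinician finds mild and stable on examination.
2. State that anyone who deteriorates, does not stabilise or is given a benzodiazepine goes to the emergency room by ambulance, regardless of history.

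The cost is one to three sentences in the protocol, a matching change to any operating procedure, and a few more emergency-room referrals. Section 12.0.0 already has a physician or nurse practitioner perform the physical examination at the visit, so the assessment needs no new staff role. No data are lost.

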18.1.5 Seizure Disorder

Participants with a known history of seizure disorder, who have a seizure while being testing, will have their testing for the day stopped. Depending upon the situation, EMS may be activated. Participants who have a singular seizure episode with full recovery will be discharged to their primary care provider. For participants who have repeated seizure episodes, EMS will be activated and the participant will be treated with short acting benzodiazepine prior to the EMS arrival. Participants will be re-contacted in 30 days to reassess their suitability for reappointment.

For all clinical presentations in sections 18.1 to 18.1.5 above:

Participants will be asked to sign an Against Medical Advice (AMA) note if they decline EMS and or transport to an emergency room or their primary care physician's office per study clinician's advice.

If a participant's study visit is terminated due to a medical problem identified on the MRV, the study team will attempt to re-contact participant within four days to follow up and determine the outcome of treatment recommendations.

18.2.0 Adverse Events & Unanticipated Problem Reporting

Adverse events associated with HANDLS study procedures are expected to occur very infrequently. Most of the potential risks associated with study procedures (see Section 1.2) are limited to mild, transient discomforts of no clinical significance. Only clinically significant adverse events will be reported to the IRB. A clinically significant adverse event will be reported as a serious adverse event if it is life threatening, causes persistent or significant disability, leads to death, or requires medical or surgical intervention to prevent a life threatening event, persistent or significant disability or death.

Anticipated minor protocol deviations and anticipated problems or adverse events, as described in sections 18.0.0 – 18.1.5 above, will be reported to the IRB annually, as part of the continuing review process.

HANDLS staff is trained to detect and respond to clinically significant adverse events. They are expected to report clinically significant adverse events to the Principal Investigator immediately or as soon as is practical. The Principal Investigators for the HANDLS Scan and the Subjective Experience of Diabetes sub-studies are also expected to report clinically significant adverse events immediately to the NIA Principal Investigators and to follow the adverse event reporting policies of their institutions. The HANDLS principal investigator will be responsible for reporting all unanticipated clinically significant adverse events to the NIEHS IRB within 7 days of receiving notification that an event occurred.

Adverse Events, protocol deviations, unanticipated problems (UP), serious adverse events, sponsor and serious, are defined as described in NIH Human Research Protections Program (HRPP) Standard Operating Procedure (SOP) #16 entitled *Reporting Requirements for Un-anticipated Problems, Adverse Events and Protocol Deviations.* All adverse events occurring during the study, including those observed by or reported to the research team, will be recorded. Serious unanticipated problems and serious protocol deviations will be reported to the IRB and clinical director as soon as possible but not more than 7 days after the principal investigator first learns of the event. Unanticipated problems defined as not serious will be reported to the IRB and clinical director as soon as possible but not more than 14 days after the PI first learns of the event. Unanticipated protocol deviations defined as not serious will be reported to the IRB as soon as possible but not more than 14 days after the PI first learns of the event. Unanticipated protocol deviations defined as not serious will be reported to the IRB as soon as possible but not more than 14 days after the PI first learns of the event. Unanticipated protocol deviations defined as not serious will be reported to the IRB as soon as possible but not more than 14 days after the PI first learns of the event. Serious adverse event deaths will be reported to the clinical director within 7 days after the PI learns of the event.

18.3.0 Reporting Waiver

Waiver of reporting to the IRB of anticipated minor protocol deviations and adverse events unless determined to be an Unanticipated Problem

The following anticipated minor deviations in the conduct of the protocol will not be reported to the IRB unless a procedural or protocol change is required:

We anticipate that not all HANDLS testing will be completed at each participant visit due to scheduling conflicts or time constraints either anticipated or unanticipated. As per protocol, tests/procedures may be rescheduled for another time as long as it is within the current testing period (wave), without compromising study data.

The following anticipated non-UP adverse events will not reported to the IRB unless associated with an Unanticipated Problem:

Syncope or near syncopal episodes, that occur before, during or after blood draws, hyperglycemic, hypoglycemic episodes, hypertensive urgency and hypotension that require minimal medical intervention, falls with minimal injury to the participant and do not require more than minimal medical intervention, Muscular strains or sprains which require minimal or no medical intervention, undiagnosed non-life threatening study results that require medical follow-up by primary care provider, such as critical laboratory values initiating a laboratory alert, EKG, Echocardiogram, ABI, DXA or MRI reports; and, any other non-life threatening or non-medically indicated treatment required event that occurs during the course of a participant's study visit.

19.0.0 Site and Clinical Safety Monitoring Plan

The NIA Clinical Research Protocol Office will perform routine visits to the HANDLS research site to ensure the safety and conduct of the study complies with 45 CFR 46 and NIA guidelines. Audits are performed to assure that clinical research is in compliance with FDA, DHHS domestic regulations, Clinical Practice Guidelines (GCP), and local and federal human subjects standards. An audit may be performed following an adverse event, protocol deviation or at the time of annual renewal. The Clinical Protocol Coordinator of the Clinical Research Protocol Office determines the frequency of monitoring visits. Participant records are randomly selected from the protocol to be audited. Targeted audits may also be carried out when there is specific concern regarding patient safety or data integrity. The principal investigator and clinical research coordinator of the study are notified at least three weeks in advance of the audit, and are asked to supply all research records and patient medical records for the audit.

The NIA Clinical Research Protocol Office (CRPO) staff and the Clinical Protocol Coordinator of the Clinical Research Protocol Office carry out the audits. Audit format follows the NCI guidelines for national cooperative group audits. Following intensive review of the research and medical records, a formal written report of the audit findings is sent to the principal investigator and the NIA Clinical Director. The site visits will be recorded in a visit log, by the monitor, and kept at the HANDLS research site.

The monitor will review various aspects of the study including, but not limited to:

(1) Compliance to the protocol;

- (2) Review of written informed consent forms for participants enrolled;
- (3) Comparison of clinic records (source documentation) to data recorded on case report forms to assure the completeness and accuracy of data collected;
- (4) Continued acceptability of facilities and staff; and,
- (5) Assessment of proper sample accountability, transfer and storage.

During the scheduled monitoring visits, source documentation will be made available to the monitor to substantiate proper informed consent procedures, adherence to protocol procedures, adequate reporting and follow-up of AEs. The Investigator (and as appropriate the research study staff) must be available to meet with the study monitor to discuss the findings from this review of Clinical Report Forms and source documents, make necessary corrections to case report form entries, respond to data clarification requests and respond to any other study-related inquiries of the monitor.

The principal investigator will be notified of any planned visit and a date will be set that is mutually agreeable. A report will be written to document all findings, solutions and discussions. The report or a follow-up letter summarizing the contents of the report will be sent to the principal investigator. Additional follow-up will be conducted by email and telephone as needed.

